12. RISK ASSESSMENT AND MITIGATION

12.1. Known and Anticipated Surgical Risks

The Sponsor-Investigator (who will also be the implanting surgeon in this study) is an experienced functional neurosurgeon with nearly 20 years' experience with deep brain stimulation. He was one of the original investigators in the first trial of DBS for movement disorders in the US ("Clinical Investigation of Deep Brain Stimulation for Treatment of Tremor Using the Medtronic Model 3382 DBS," 1996-1999). He will perform the surgical procedures in this study using his standard technique, developed in over 600 successful implants.

12.2. Device-Related and Therapy-Related Risks

Co-Investigators [name], [name], and [name] were all involved in the original trial of CT-DBS for the treatment of the minimally conscious state (MCS). Drs. [name] and [name] are world experts in traumatic brain injury. They will direct parameter selection for DBS programming and will consult on targeting of the CT along with Drs. [name] and [name], both of whom have extensive experience in targeting this region.

The inclusion/exclusion criteria have been developed to exclude participants with concurrent illnesses that could increase the risk of DBS placement, as well as major developmental, neurologic, psychiatric or substance use disorders that may confound interpretation of results. Participants for whom DBS implants are contraindicated are excluded from study participation (e.g., a medical condition requiring MRI, and/or exposure to diathermy).

Participants will be counseled that they are not to undergo an MRI examination or shortwave diathermy as long as the DBS system is implanted.

12.3. Protocol for Managing Suicidal Ideation and Intent

All study personnel will be provided with the following protocol for managing suicidal ideation and intent. Participants will be closely monitored for any suicidal thoughts or plans during all study interactions, including telephone calls and in-person visits.

If the participant endorses an item suggesting suicidal ideation on any self-report questionnaire, or reports suicidal ideation at any time during participation in the study, immediately administer questions 1 and 2 from the Columbia Suicide Severity Rating Scale (CSSRS). Proceed with administering items as needed according to the instructions for that scale. Based on the participant's responses, follow one of the following procedures.

1. **Scenario 1: Participant responds “no” to question 2 on C-SSRS (“Have you actually had any thoughts of killing yourself?”)**

Empathize with how hard things have been for them and let them know that it is not unusual for people to have these thoughts when they have experienced TBI. Encourage them to talk to a family member or friend when they feel this way. Also provide them with a crisis line number and encourage them to phone if they ever start thinking about actually killing themselves. Proceed with the study protocol.

2. **Scenario 2: Participant responds “yes” to question 2 on C-SSRS (“Have you actually had any thoughts of killing yourself?”) AND answers “no” to question 3 (“Have you been thinking about how you might kill yourself?”)**

Empathize with how hard things have been for them and let them know that it is not unusual for people to have these thoughts when they have experienced TBI. Encourage them to talk to a family member or friend when they feel this way. Also provide them with a crisis line number and encourage them to phone if they ever start thinking about actually killing themselves. Proceed with the study protocol.

3. **Scenario 3: Participant responds “yes” to question 3 on C-SSRS (“Have you been thinking about how you might kill yourself?”) AND answers “no” to question 4 (“Have you had these thoughts and had some intention of acting on them?”).**

Discuss a safety plan with the participant. If you are meeting with the participant in person, have them complete the safety plan themselves, providing guidance as necessary.

Then have the participant sign it and ask the study physician or a licensed psychologist on the team to review the plan with them. Provide them with the crisis line information by writing it on the safety plan. If you are talking with the person by phone, go over the safety plan, asking them to generate responses to the items, while providing guidance as necessary. Record their responses and then ask the study physician or a licensed psychologist on the team to review the plan with them. Send them a copy by mail, provide the contact information for the crisis line verbally over the phone and write it on the safety plan before mailing.

4. **Scenario 4: Participant responds “yes” to question 3 on C-SSRS (“Have you been thinking about how you might kill yourself?”) AND either answers “yes” to question 4 (“Have you had these thoughts and had some intention of acting on them?”) or is equivocal regarding whether they intend to act on their thoughts.**

Ensure that they are safe at the moment. This means that they are not in imminent danger of harming themselves and do not have guns, knives or other weapons available to use. If you cannot deem that they are safe, ask their permission to speak with a family member who is with them. Tell the family member that they should stay with the patient and should make sure that they are safe, provide them with the crisis line number, advise them to take the person to an emergency room if possible, and advise them to call 911 if they fear that they cannot stop the person from hurting themselves and cannot talk them into going to the emergency room. If there is no family member present, or they refuse to have you speak with one, and you cannot deem that they are safe, maintain them on the line and ask the study physician, another research team member or an administrative assistant to call 911 and ask that the police visit the participant at their current location. Meanwhile, ask the participants’ permission to connect them to a crisis line so that they can talk with someone who is trained to help them through the crisis. If they agree, connect them to the crisis line.

NOTE: Occasionally, someone may withhold permission for you to transfer them to a crisis line. If this refusal appears to be due to fear, uncertainty, or embarrassment, then talk them through the reasons for the crisis line and ask their permission again. If they still refuse, or if they appear to simply want to stay on the line talking with you, tell them that for their own safety, you need to connect them to the crisis line. Ask them to stay on hold while you dial the crisis line. Make sure that they have your telephone number so that they can call you back in case you are disconnected. You may call them back if you are disconnected. If you are unable to reach them, and you deem that they are in imminent danger of harming themselves, then call 911 and ask the police to visit the person at their current location.

NOTE: The same protocol can be applied to a person who endorses suicidal ideation and intent during an on-site assessment. Simply have them call the crisis line from a nearby office.

REMEMBER TO DOCUMENT EACH STEP THAT YOU PERFORM, HAVE THE SPONSOR-INVESTIGATOR OR HIS DESIGNEE (EG, STUDY PHYSICIAN, PSYCHOLOGIST) REVIEW THE SAFETY PLAN AND PLACE IT IN THE PARTICIPANTS’ RESEARCH FILE.

The process for connecting on-line telephone participant to crisis line:

While on the phone with the participant, ask them to hold while you connect them to the crisis line (or use the conference-calling feature, if available):

Crisis Line #: [name] National Suicide Prevention Lifeline
[name] (Spanish)

Be sure that they have been connected to a crisis counselor before hanging up.

13. Administrative Requirements, including Investigator Responsibilities

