9.3. Serious Adverse Events (SAEs)

A serious adverse event is one that meets any of the following criteria (ICH Good Clinical Practice Guideline, April 1996, Section 1.50):

- Results in death
- Is life threatening
- Requires inpatient hospitalization or prolongation of existing hospitalization
- Results in persistent or significant disability/incapacity
- Is a congenital anomaly/birth defect

Events that do not meet these criteria are considered non-serious

A planned hospitalization for pre-existing condition, or a procedure required by the Clinical Investigation Plan, without a serious deterioration in health, is not considered to be a serious adverse event.

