9.5.1. Reporting Serious Adverse Events

The Sponsor-Investigator will direct all study personnel to inform him as soon as possible (within 24 hours) of any serious adverse event. If necessary, study personnel may communicate by telephone or e-mail, and follow-up later with completed case report forms. The Sponsor-Investigator will conduct an evaluation of the event and if it is determined to be a UADE, it will be reported as described in the following section.

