10. CLINICAL OVERSIGHT COMMITTEE

It is the responsibility of the Sponsor-Investigator to oversee the safety of the study participants. This includes careful assessment and appropriate reporting of adverse events as noted above.

In addition, a Clinical Oversight Committee (COC) has been appointed to conduct ongoing reviews of the safety of the Study and make recommendations regarding changes to the risk/benefit of the Study, including recommendations to discontinue new patient enrollments or discontinue the Study. The COC will review all SAEs as they occur and will conduct routine reviews at least quarterly throughout the study.

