10.1. Medical Monitor

An Independent Medical Monitor has been designated for this study to regularly assess reports of unanticipated study-related events. Once per quarter the Medical Monitor will review reports of any study-related unanticipated adverse events. The Clinical Oversight Committee will convene an ad hoc meeting to review any report of an unanticipated adverse event that is both study-related and serious.

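### Section 12.3 gives a participant who reports thoughts of killing themselves the instruction written for one who denies them, and does not direct staff to tell a clinician

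*Combined protocol and SAP*

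**What the plan says.** Section 12.3 is issued to all study personnel. It applies when a participant endorses a suicidality item on a questionnaire or "reports suicidal ideation at any time during participation in the study", so it covers visits and telephone calls, before and after surgery. Under 7.3 the C-SSRS is given at the pre-surgery baseline, and at follow-up only if PHQ-9 question 9 is positive.

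Scenarios 1 and 2 share one text: empathize, encourage contact with family or a friend, give a crisis line number, then "encourage them to phone if they ever start thinking about actually killing themselves. Proceed with the study protocol". Scenario 3 adds a safety plan and has staff "ask the study physician or a licensed psychologist on the team to review the plan with them". Scenario 4 deals with immediate danger. A closing reminder asks staff to document each step and "HAVE THE SPONSOR-INVESTIGATOR OR HIS DESIGNEE (EG, STUDY PHYSICIAN, PSYCHOLOGIST) REVIEW THE SAFETY PLAN".

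Elsewhere, study personnel must "inform him as soon as possible (within 24 hours) of any serious adverse event" (9.5.1). Section 9.3 lists five criteria for seriousness and adds: "Events that do not meet these criteria are considered non-serious". On oversight, section 10 says "The COC will review all SAEs as they occur and will conduct routine reviews at least quarterly throughout the study", and 10.1 says "Once per quarter the Medical Monitor will review reports of any study-related unanticipated adverse events". Section 9.4.1 lists suicidal ideation among the effects expected from stimulation.

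**The concern.** A ladder with four rungs should respond differently when the answer changes from no to yes. Here the response is the same, and the message does not fit: a participant who has just reported thoughts of killing themselves is told to call should such thoughts begin. Either the text was carried over from Scenario 1 by mistake, or one response was meant for both answers and the wording was never adapted. Both cases need correcting.

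The missing clinician matters more than the wording. Because 12.3 is addressed to all personnel, the person hearing the answer may not be clinically qualified, so clinician involvement has to be written down to be assured. The protocol itself expects that stimulation may cause suicidal ideation. During the 21-day blinded phase, breaking the blind depends on the treating physician's view (9.5), and a physician who has not been told cannot form one. Before surgery, the sponsor-investigator's eligibility judgment likewise depends on the answer reaching him.

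**Working it through.** No power, alpha or sample-size figure bears on this point. The check compares texts and traces what each route does with a Scenario 2 answer.

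**Step 1: the two instructions.** An exact string comparison of the Scenario 1 and Scenario 2 texts finds them identical, at 71 words each. A search of that text for physician, psychologist, clinician, refer, sponsor and safety plan finds none of them.

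**Step 2: the ladder side by side.**

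| Scenario | Trigger | Action | Clinician review written? |
|---|---|---|---|
| 1 | No to question 2 | Support, crisis line, proceed | No |
| 2 | Yes to question 2, no to question 3 | Same 71 words | No |
| 3 | Yes to question 3, no to question 4 | Safety plan | Yes, of the plan |
| 4 | Yes to question 3; yes or equivocal on question 4 | Secure safety, family, crisis line, emergency services | Not as such; the study physician is one of several people who may place the emergency call |

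The closing reminder does not reach Scenario 2. It requires review of a safety plan, and Scenario 2 creates none. Documenting the steps produces a record, not a notification.

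**Step 3: do other routes supply a prompt notice?**

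- *Serious adverse event notice (9.5.1, 9.3).* The 24 hours apply to serious events. Ideation without method or intent would not ordinarily meet any of the five criteria. That is a reading of the criteria; the protocol does not say so.
- *Adverse event form (9.1, 9.5).* New or worsened ideation during the investigation is recorded, before or after implantation, with severity, relatedness and any treatment. No deadline is set for a non-serious event. Ideation already present at baseline and unchanged is outside the definition.
- *Medical Monitor (10.1).* Review is quarterly and limited to unanticipated study-related events. Suicidal ideation is listed as anticipated, although 9.4.2 also treats frequency or severity above the labeling as unanticipated.
- *Clinical Oversight Committee (10).* It sees serious events as they occur and otherwise reviews at least quarterly.

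None of these is a prompt notice to a clinician set off by the answer.

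**Step 4: reach.** The blinded phase is 191 − 170 = 205 − 184 = 219 − 198 = 21 days in the three cohorts (6.3). Section 6.6.1 reports on the first 5 patients of 6, so 6 − 5 = 1 implant remained when that text was written. The pre-implant part of any change therefore reaches about one participant, while the rewording reaches everyone still in follow-up. The documents give neither that number nor a rate of ideation. Scheduled assessments would be the wrong denominator, because 12.3 applies at any contact.

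**The case against.** The strongest reply is that a graded response is legitimate and that where clinician review begins is a judgment. Scenario 2 is not empty: it gives a crisis line, encourages family contact and must be documented. That stands as a defence of grading. It does not defend a sentence that contradicts its own trigger, or silence about whom to tell.

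A reader might go further than the documents allow in four ways.

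- *That a pre-surgery yes has no route to an eligibility decision.* It has one. The C-SSRS belongs to the pre-surgery baseline (7.3), and eligibility stays open until pre-operative tests are complete (6.2). The exclusions cover severe uncontrolled psychiatric disorder and any finding the PI judges to raise risk (6.1.2), and the sponsor-investigator may fail a candidate on clinical judgment (6.5). The instruction to proceed does not override these. What is missing is a prompt that carries this answer to the person judging.
- *That adverse event recording starts only at implantation.* The definition in 9.1 runs over the whole clinical investigation and does not require an implant.
- *That switching stimulation off is known to be dangerous.* Section 9.4.1 lists rebound worsening on discontinuation, but 6.3 states that no safety issue with withdrawal is currently known. The documents report no case linking withdrawal to ideation.
- *That listing ideation as anticipated always removes it from the Medical Monitor.* Section 9.4.2 leaves room for excess frequency or severity, though the review remains quarterly.

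**Conclusion.** The point holds in a narrow form. One of four scenarios carries an instruction that contradicts its own trigger and does not direct staff to inform a clinician, at any contact. This is a written rule that misfires, not a missing detail, and it should be corrected.

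Its size in participants cannot be stated, for the reasons given under reach. There is no numerical effect on the primary outcome or on the descriptive analysis.

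The conclusion rests on two assumptions: that staff follow 12.3 as written, and that ideation without method or intent is normally classed as non-serious. If the site already tells a physician about every such answer, the gap lies in the document rather than in practice, and the amendment would record what is done. The existing eligibility safeguards and adverse event recording are sound as far as they go and are not faulted here.

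**What to change.** Rewrite Scenario 2 in 12.3 for all contacts, before and after implantation.

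1. Replace the crisis-line sentence with wording for someone who already has these thoughts, for example advice to call now, or whenever the thoughts return or become stronger.
2. State that any yes to C-SSRS question 2 is reported promptly to the study physician or licensed psychologist. Twenty-four hours is a suggested window, borrowed from 9.5.1; the documents do not derive one for this tier.
3. If the answer comes before implantation, include the sponsor-investigator in that notice, so that the eligibility judgment already provided for in 6.1.2, 6.2 and 6.5 is made with knowledge of it. This does not force exclusion.

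No new instrument, data item or staff role is needed, since 12.3 already names the clinicians. The cost is some clinician time for each Scenario 2 answer. Section 13.5 requires written FDA and IRB approval if the change counts as substantive, with the IRB able to expedite minor changes.

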7.3. Psychological Health (self-report)

- **Patient Health Questionnaire-9 (PHQ-9) {Kroenke, 2001, The PHQ-9}**. The Participant Health Questionnaire 9 is a standardized assessment instrument designed to screen, diagnose, monitor, and measure the severity of depression.
- **Columbia Suicide Severity Rating Scale (C-SSRS) {Posner, 2011, The Columbia-Suicide Severity Rating Scale: initial validity and internal consistency findings from three multisite studies with adolescents and adults}**. The C-SSRS is a standardized assessment instrument designed to assess the presence and severity of suicidal ideation and behavior, identify those at risk, and track response to treatment. It has three main sections that evaluate suicidal ideation, the intensity of ideation and suicidal behavior. The first section, suicidal ideation, assesses risk ranging from a death wish or unspecific suicidal thoughts to active ideation with specific plans. In the second section the severity of ideation is evaluated and takes into account the frequency, duration and controllability of suicidal thoughts as well as environmental and cultural deterrents and reasons for suicidal ideation. The third section evaluates actual suicidal behavior and asks if there was an actual attempt, interrupted attempt, aborted attempt or preparatory acts of behavior. It also asks whether there was active suicidal behavior at the time of assessment and, finally, if suicide was completed. A fourth section is only answered in case there was / were suicidal attempts and measures the lethality and potential lethality of each suicidal attempt and respective dates. The CCSRS is a widely-used instrument and is currently being utilized in other first-in-man DBS clinical trials. The C-SSRS will be administered during the pre-surgery baseline assessment and then at any follow-up visit **only if the participant screens positive for suicidal ideation/behavior on the PHQ-9** (i.e. score ≥ 1 on question 9).

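### Section 12.3 routes suicide risk on C-SSRS questions 2, 3 and 4 only, so recent suicidal behaviour reported at a follow-up visit can lead to continuation with no clinician step required by that section

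*Combined protocol and SAP*

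**What the plan says.** Section 7.3 describes what the C-SSRS collects. Its third section "asks if there was an actual attempt, interrupted attempt, aborted attempt or preparatory acts of behavior". The description continues: "It also asks whether there was active suicidal behavior at the time of assessment". The scale is given at the pre-surgery baseline and then at follow-up visits "only if the participant screens positive for suicidal ideation/behavior on the PHQ-9", which the section defines as a score of at least 1 on question 9.

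Section 12.3 is triggered when a participant endorses or reports suicidal ideation. Staff ask C-SSRS questions 1 and 2, then "Proceed with administering items as needed according to the instructions for that scale". They then follow one of four scenarios:

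- Scenario 1 (question 2 no) and Scenario 2 (question 2 yes, question 3 no) prescribe an empathic response, encouragement to talk to someone close and a crisis line number. Both end in "Proceed with the study protocol".
- Scenario 3 (question 3 yes, question 4 no) requires a safety plan, and staff must "ask the study physician or a licensed psychologist on the team to review the plan with them".
- Scenario 4 (question 3 yes, and question 4 yes or the participant "is equivocal regarding whether they intend to act on their thoughts") sets emergency steps.

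A closing reminder tells staff to document each step and to have the Sponsor-Investigator or a designee "REVIEW THE SAFETY PLAN AND PLACE IT IN THE" participant's research file.

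**The concern.** The protocol administers an instrument that asks about suicidal behaviour, but its only suicide-response script gives staff nothing to do with a positive answer. A participant can deny thoughts of killing themselves, or admit them while denying thoughts of method, and still report a recent aborted attempt or preparatory act. Followed literally, the script then has staff continue the study without calling a clinician.

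This also conflicts with the plan's own threshold. Scenario 3 gives physician or psychologist review to someone who has thought about method and has no intent. Reported behaviour with question 2 or question 3 answered no receives less.

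What is at stake is participant safety. Section 9.4.1 lists suicidal ideation among the known or expected effects of stimulation, and suicide attempt among the anticipated adverse events.

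**Working it through.** The plan gives no figure to reproduce, so the check is a reading of the decision table.

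**Inputs.** The scenario criteria and responses come from section 12.3, and the behaviour items from section 7.3. The setting is a follow-up visit at which the C-SSRS is given because PHQ-9 question 9 scored 1 or more.

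**Step 1: the table.**

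| Scenario | Selected by | Uses a behaviour answer? | Clinician or emergency step in 12.3 |
|---|---|---|---|
| 1 | Q2 no | No | None; continue |
| 2 | Q2 yes, Q3 no | No | None; continue |
| 3 | Q3 yes, Q4 no | No | Safety plan, reviewed by physician or psychologist |
| 4 | Q3 yes, Q4 yes or equivocal | No | Emergency steps |

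**Step 2: cross the scenarios with behaviour.** Four scenarios by behaviour reported or not gives 4 × 2 = 8 cells. Within each scenario the two cells carry the same response, so behaviour alters the response in 0 of 4. Of the 4 cells with behaviour reported, 2 (Scenarios 1 and 2) end in continuation. These are counts of rules, not probabilities; the documents give no event rate.

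**Step 3: does the closing reminder fill the gap?** It calls for review of the safety plan. Scenarios 1 and 2 do not create one, so there is nothing for the reviewer to receive.

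**Step 4: do other sections supply the missing step?**

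- Section 9.5 requires any adverse clinical event to be recorded and rated. That is documentation and does not set an immediate response.
- Section 9.5.1 brings the Sponsor-Investigator in within 24 hours, and section 10 brings in the Clinical Oversight Committee, for events that are serious under section 9.3. An aborted attempt or preparatory act may meet none of those criteria.
- The Medical Monitor (section 10.1) reviews unanticipated study-related events. Suicidal ideation and suicide attempt are on the anticipated lists in section 9.4.1, so they would ordinarily fall outside that review.
- Unscheduled visits (6.12) and investigator withdrawal (8) depend on an investigator who has been told.

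None of these prescribes a same-day clinical response to reported behaviour.

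**Step 5: remaining exposure.** Six participants are planned (Synopsis). Section 6.6.1 refers to results from the first 5 and to the final patient still to be implanted, so 6 − 5 = 1 implant is outstanding. That participant has 12 to 14 months on study (Synopsis). Any remaining follow-up of the first 5 adds to this.

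**The case against.** The strongest reply is that section 12.3 is titled for ideation and intent, while an attempt is an event and events have their own route. Suicide attempt is an anticipated adverse event by name. It must be recorded, rated for severity and relatedness and, if serious, reported to the Sponsor-Investigator within 24 hours and reviewed by the committee as it occurs. Staff must also monitor closely for suicidal thoughts at every interaction, and severe uncontrolled depression is excluded at entry. On this view, continuing the protocol means continuing one that contains those duties.

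Much of this stands. A reader might infer that reported behaviour would receive no clinician review at all, and the documents do not support that. The claim is only that 12.3 requires no clinician step. What survives is immediacy, and the aborted attempts and preparatory acts that may not count as serious.

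Two further readings are tempting. One is that stated or equivocal intent can fall into Scenario 2 when question 3 is answered no. The other is that question 2 no with question 3 yes matches two scenarios at once. Both depend on which items are asked after a no. Section 12.3 leaves that to the scale's own instructions, which the documents do not reproduce. If later items are skipped after a no, neither problem arises, so neither is established.

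It is also fair to say that the firm ground is limited to visits where section 7.3 has the scale administered. For telephone contacts, whether the behaviour items are asked depends on the same unseen instructions.

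**Conclusion.** The point holds in this limited form. At a follow-up visit where the C-SSRS is given, recent suicidal behaviour with question 2 no, or with question 2 yes and question 3 no, is routed to continuation with no clinician step required by section 12.3. This is an instruction to continue, not merely missing detail.

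It rests on two assumptions: that the behaviour section described in 7.3 is completed at those visits, and that staff follow the script as written. In practice clinical judgement may intervene. The word recent is this review's; the documents set no look-back window, and remote attempts recorded at baseline are not part of the point.

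Severity is minor to moderate. No endpoint or analysis is affected and few participants remain exposed, but a missed case could be fatal and the repair is short. It is best treated as a cheap improvement.

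**What to change.** Add one branch to section 12.3. Any current or recent suicidal behaviour (an actual, interrupted or aborted attempt, or a preparatory act), whatever the answers to questions 2 to 4, leads to a safety plan and same-day review by the study physician or licensed psychologist already on the team. This is in addition to any Scenario 4 emergency steps. The clinical team should set the look-back window, and remote attempts recorded at baseline should be excluded.

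The safety plan also gives the closing reminder something to act on in Scenarios 1 and 2.

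The cost is an occasional same-day clinician contact, brief retraining and, if the change is judged substantive under section 13.5, written FDA and IRB approval. No scheduled visits are added.
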